**STUDY SUMMARY**

Study Title	A Proof-of-Concept Study of The Complete Vocal Technique (CVT), a pedagogic technique used for Performers, in Improving the Voice and Vocal Function in Patients with Muscle Tension Dysphonia using Telehealth
Internal ref. no. (or short title)	CVT4MTD
Study Design	Proof-of-concept study
Study Participants	Patients with Type I-III Muscle Tension Dysphonia voice disorder
Planned Size of Sample (if applicable)	Ten
Follow up duration (if applicable)	Eight weeks
Planned Study Period	28/02/2022 to 26/08/2022
Research Question/Aim(s)	
 
1) The principal research question is: “Can the approach used in the pedagogic Complete Vocal Technique (CVT) to optimise voice production in singers and performers be applied to patients with Muscle Tension Dysphonia to improve vocal symptoms, vocal function, and meet patient treatment goals using a Telepractice medium?”
 
2) Is the CVT voice therapy (CVT-VT) approach using Telepractice perceived as beneficial by patients, the study SLT-V and study CVT-P?
 
3) Does the CVT-VT approach differ or provide additional benefits to traditional SLT-VT methods in the treatment for patients with MTD
 

SHORT TITLE/ACRONYM: CVT4MTD

IRAS:306954

**FUNDING AND SUPPORT IN KIND**

FUNDER(S) (Names and contact details of ALL organisations providing funding and/or support in kind for this study)	DETAILS OF FINANCIAL AND NON FINANCIAL SUPPORT GIVEN
Innovation Fund Denmark	(Total Grant: £222,685 NUH grant allocation £55,903)
Complete Vocal Institute	None

**ROLE OF STUDY SPONSOR AND FUNDER**

The sponsor, Nottingham University Hospitals has overall responsibility for the initiation and management of the study. The study sponsor will monitor the study conduct against applicable regulatory standards. The study sponsor and study funder will have no role in the design, data analysis, interpretation, manuscript writing and dissemination of the results. The sponsor and funders will be consulted for the final decision/s regarding any aspects of this study.

SHORT TITLE/ACRONYM: CVT4MTD

IRAS:306954

## ROLES AND RESPONSIBILITIES OF STUDY MANAGEMENT COMMITTEES/GROUPS & INDIVIDUALS

There will be no formal Study Steering Group as this is a pilot/feasibility study. PPI has been sought and the study progress will be reviewed monthly by the study team [name], [name] and [name].

**STUDY FLOW CHART**

**CONFIDENTIAL**

Page 7 of 39

IRAS 306954; 19ET004 Protocol V2.1 28 Mar 2022

[figure not shown]
SHORT TITLE/ACRONYM: CVT4MTD

IRAS:306954

Gantt chart:

[figure not shown]
Task	Description	Year 2022			
		Q1	Q2	Q3	Q4
1	IRAS submission	X			
2	Recruit patients		X	X	
3	Treat patients		X	X	
4	Evaluate metrics			X	X

Flow diagram:

[figure not shown]
**CONFIDENTIAL**

**Face-to-face research voice clinic joint assessment by study Laryngologist and SLT (t=0):**

- Patients sign consent to take part in study ([Appendix A](#))
- Confirmation of history and laryngostroboscopic
- Questionnaires completed
- Acoustic and EGG recordings + MPT made ([Appendix B-Acoustic and EGG measures and justification](#))
- All patients given Indirect voice therapy ([Appendix C](#))
- Arrangements for testing of video link made

SHORT TITLE/ACRONYM: CVT4MTD

IRAS:306954

### Treating CVT Practitioner (t=0 to t=6)

Up to 6 sessions (45-60 mins) given online over a total of 6/52

- Medical/SLT assessment documentation available to Practitioner
- Assessment by treating Practitioner and treatment plan including goals agreed with patient
- Structured proforma documenting session goals, and % time of therapy used in each session completed at end of each session to form part of treatment record
- Observation by study SLT-VT, and/or recording of sessions
- Review of progress (log of treatment and study SLT -V observations where performed) by study SLT-V, study CVT-P and Laryngologist after 2 and 4 therapy sessions

If concerns about suitability of treatment for patient, they may exit the study after agreement between study team and patient

### Final face to face session (t=8): Joint assessment by study Laryngologist and SLT

- Rating of achievement in obtaining goals by patient, study SLT-VT, study CVT-P and treating CVT-P
- Repeat questionnaires
- Repeat acoustic/EGG voice recordings + MPT
- (optional repeat stroboscopic laryngeal examination to assess confirmatory improvement in laryngeal appearance and recording of 'no damage' from treatment)

## 1. BACKGROUND

### Muscle Tension Dysphonia

Voice problems (dysphonia) affect one in 13 adults annually, causes a major impact on quality of life and livelihood and is a substantial healthcare burden (Lyberg-Åhlander, Rydell et al. 2019). It is more common in women and in those with vocally demanding professions and the elderly. The causes of voice problems can be broadly divided in to 'organic' and non-organic'. Examples of organic causes are nodules, polyps, cancers, nerve weakness and laryngitis (McGlashan, Costello et al. 2007). Non-organic causes, also known as primary Muscle Tension Dysphonia (MTD) are due to an imbalance of breathing mechanism and/or tightness of the muscles of the voice box or throat, which leads to a decompensation of the voice and the patient becoming symptomatic and dysphonic (Altman, Atkinson et al. 2005); (Mathieson, Hirani et al. 2009);(Van Houtte, Van Lierde et al. 2011). MTD can also be secondary to organic pathology which needs to be excluded before a diagnosis of primary

**CONFIDENTIAL**

Page 10 of 39

SHORT TITLE/ACRONYM: CVT4MTD

IRAS:306954

MTD is made. There are different presenting patterns of primary MTD but generally there are six recognisable patterns both in their presenting symptoms, voice quality and on laryngeal appearance on endoscopy. Three types (MTD patterns I-III) are more related to ineffective voice use, also known as 'voice abuse' or 'voice misuse', while the other three types (MTD patterns IV-VI) have a psychological basis (Belisle and Morrison (1983); (Koufman and Blalock 1991);(Harris 2018);(Rammage, Morrison et al. 2001);(Hsiung and Hsiao 2004);(Koufman 2014); (Rammage, Morrison et al. 2001). MTD forms the largest group of dysphonic patients seeking treatment in the UK accounting for 10-40% of referrals (Carding 2003, Dromey, Nissen et al. 2008).

Patients with dysphonia have problems with one or more of the following: hoarseness, abnormal pitch or loudness, variability in quality or control of their voice. In the UK, patients with persistent or unexplained hoarseness who are over the age of 45 are referred under the two-week wait (2WW) cancer referral process (NICE 2015, Douglas, Middleton et al. 2021). In other cases, referral to an Ear, Nose and Throat (ENT) benign voice service is usually considered if the dysphonia persists for more than six weeks, it has not improved with simple measures such as voice rest, reducing irritation to the vocal cords and drinking plenty of fluids (known as vocal hygiene advice) or it is impacting significantly on the patient's work or their social life. In practice patients with MTD may come through both the 2WW and benign voice pathways.

#### **Diagnosis and traditional treatment of MTD (see Appendix A for more details)**

Patients are diagnosed with MTD by an ENT surgeon from the history of their vocal complaint and by excluding an organic cause on examination of their voice box (larynx) with a small flexible video camera passed through their nose. Treatment is with voice therapy given by a Speech & Language Therapist who has specialised in voice disorders (SLT-V) (MacKenzie, Millar et al. 2001);(Wilson, Deary et al. 2002, Roy 2008). Voice therapy consists of two main types: Indirect Voice Therapy and Direct Voice Therapy (Van Stan, Roy et al. 2015) and is guided by advice from professional organisations such as Royal College of Speech and Language Therapists Clinical Guidelines (Taylor-Goh 2017) and the American Speech-Language-Hearing Association (ASHA) Clinical Practice Guideline: hoarseness (dysphonia) (Schwartz, Cohen et al. 2009). **Indirect therapy** consists of education, information, vocal hygiene and stress management (Roy, et al., 2001; Thomas & Stemple, 2007). **Direct therapy** consists of establishing healthy voice production (Colton & Casper, 2011; Stemple, 2000) by rebalancing the three subsystems of voice production namely breathing (respiration), voice production (phonation) and more efficient use of resonance (Guenther, Ghosh et al. 2006, Stemple, Roy et al. 2020).

The aim of voice therapy is generally to (a) return the patient's voice to normal or as best as possible within their anatomic and physiologic capabilities and (b) to satisfy the patient's occupational, social and emotional vocal needs (Aronson and Bless 2009) and (c) promote habit changes that will ensure voice improvement will be maintained (Mathieson 2001). Therapeutic goals should be specific and

**CONFIDENTIAL**

Page 11 of 39

SHORT TITLE/ACRONYM: CVT4MTD

IRAS:306954

determined by the patient prior to therapy to empower the patient in shared decision making with the aim of improving motivation and compliance (Shewell 2009, Titze and Verdolini Abbott 2013, Titze, Riede et al. 2018). In addition, the aim should be maximum improvement in the minimum time ((Mathieson 2001) page 372).

Many SLT-Vs use traditional, hierarchical, therapy techniques focusing in the early stages on postural and relaxation techniques, followed by breathing exercises, voicing and resonance work with final consolidation and review (Harris 2018). Often the numerous methods of treatment are used, often targeted on abnormal findings on clinical examination (Jones 2016) (see Table 1).

**Table 1 (modified from Jones, 2016). Note CVT would be expected to address each aim**

AIM	Silent inspiration	Silent giggles/ laugh	Yawn, sigh	Accent method	Breath before tone	Plosive consonant closure	Glottal onset	Simultaneous onset	Humming	Glottal fry/ creak	Sob/ whine	Chewing	Vocal function exercises	Laryngeal manipulation	Twang	Siren	SOVT	Resonance work
Reduce pharyngeal constriction/ lower larynx		x	x							x	x		x				x	
Reduce glottic/ false vocal fold constriction	x	x		x	x			x	x		x							
Reduce antero-posterior or posterior-anterior constriction			x	x							x			x				
Improve vocal fold closure/ establish modal voice				x		x	x	x	x	x	x		x		x			

SHORT TITLE/ACRONYM: CVT4MTD

IRAS:306954

*patients and providers are separated by distance... (it) can contribute to achieving universal health coverage by improving access for patients to quality, cost-effective, health services wherever they may be*" (<https://www.who.int/gho/goe/telehealth/en>). Prior to the COVID pandemic, telepractice had been used by Speech and Language therapists mostly for geographical reasons and difficulties in patients' attending outpatient clinics. There are relatively few studies in its use for voice disorders (Reynolds, Vick et al. 2009) and most studies on effectiveness have involved small cohorts of patients with a range of voice pathologies such as Parkinson's disease (Mashima, Birkmire-Peters et al. 1999, Mashima, Birkmire-Peters et al. 2003, Tindall, Huebner et al. 2008, Constantinescu, Theodoros et al. 2011, Fu, Theodoros et al. 2015). There are few Randomised Controlled Studies comparing face-to-face versus Telepractice and only one study of MTD patients using the same voice therapy technique (Flow phonation). This showed no significant difference in outcome between the two methods of delivery (Rangarathnam, McCullough et al. 2015). Disadvantages of telepractice for voice therapy include generic problems with technology, patient environmental and cultural considerations, some instructional and practical issues with inability to deliver more 'hands-on' techniques such as laryngeal manipulation (Keck and Doarn 2014, Molini-Avejonas, Rondon-Melo et al. 2015, Edwards-Gaither 2018, Lin, Chien et al. 2020).

### **The Complete Vocal Technique**

(Aaen, McGlashan et al. 2019, Aaen, McGlashan et al. 2021)The Complete Vocal Technique (CVT) is primarily a method of teaching singers and singing teachers to produce any singing or speaking voice sound that is required. It has been used for over 35 years particularly in Europe and CVT practitioners (CVT-P) undergo an accredited 3-year training programme. It uses a hierarchical approach with terminology that is clearly defined and supported with scientific characterisation (McGlashan, Thuesen et al. 2017, Thuesen, McGlashan et al. 2017, Aaen, McGlashan et al. 2019, Aaen, McGlashan et al. 2021, Leppävuori, Lammentausta et al. 2021). It is based on four key building blocks enabling the singer to produce vocal sounds regardless of genre of music (Complete Vocal Institute, 2015; Sadolin, 2017). The first building block in CVT training is to ensure a healthy voice is produced by adopting the three overall principles: adequate support for the voice, use of a degree of twang ('necessary twang') and avoidance of jaw protrusion and tightening of the lips. Secondly one of four main vocal modes (Neutral, Curbing, Overdrive and Edge) is chosen which provides a set up for the larynx and the choice is determined by vocal demand (loudness, pitch range, vowel and genre 'norm' (vocal style) that is required, Neutral relates to normal conversational voice while the Curbing is a medium loud voice. Overdrive can be used for voice projection up to a shout loudness, while Edge can be used for a yelling quality. It would be expected that training in Neutral and Overdrive would allow good vocal function for most social situations. The third is then to adjust the degree of sound colour (from dark to light) mostly by lowering and raising the larynx. The fourth element is to add specific vocal effects such as vibrato, ornamentation, distortion etc., which can be added once the first three

**CONFIDENTIAL**

Page 14 of 39

IRAS 306954; 19ET004 Protocol V2.1 28 Mar 2022

SHORT TITLE/ACRONYM: CVT4MTD

IRAS:306954

have been achieved. In this way the precise sound required by the singer can be fashioned in any style or genre of music. The principles can and have been applied to training the speaking voice and provide a recipe for producing any desired voice quality for any environmental situation. A similar approach, that has not been widely adopted, has also been described by Grillo (Grillo 2012) whereby the aim is not to support the production of 'one voice', as is frequently the case with traditional SLT-VT, but to provide the patient with a range of 'new' voices to meet their vocal needs.

Training programmes using CVT methodology have been developed to enable singers and singing teachers to improve their singing voice, achieve vocal goals and overcome technical issues many of which are due to unintentional hyper-constrictive muscle activity within the larynx and vocal tract. Voice therapy based on CVT principles (CVT voice therapy (CVT-VT)) has also been applied to professional speaking voice users and singers presenting with acute vocal problems leading to hoarseness or loss of voice when time is of the essence in getting a vocalist back to performing. This CVT-VT can help with deconstriction and improved voice production and projection. Although widely used by CVT-Ps CVT-VT has not been formally evaluated in performers or applied to non-performers although the principles of treatment of good voice production and deconstriction are applicable to both groups.

The application of telepractice during the COVID pandemic has also become a necessity in teaching singing teachers including at the Complete Vocal Institute (CVI) in Denmark where almost all tuition is now delivered on-line. Informal feedback from singers has been positive ([name], personal communication) with many advantages (reduction in cost and travel time) outweighing the disadvantages (peer support of singers in small groups, some technical issues). It is likely a complete return to previous methods of delivery of SLT and CVT practice will not happen after the COVID-19 pandemic with the adoption of the new methods of service delivery for both. However, ultimately a hybrid method of face-to-face and telepractice service may become the preferred method of practice.

## 2. RATIONALE

Although traditional voice therapy techniques are generally successful in improving dysphonia there is a general lack of good quality studies on its efficacy (Bos-Clark and Carding 2017). SLT-VTs have used mainly voice quality or physiological approaches (see Table 1) to guide therapy. Treatment studies have frequently focused on changes in outcome measures without adequate description and classification of the therapeutic processes that caused the measurement changes (Van Stan, Roy et al. 2015). This makes it difficult to determine why patients improve, which therapy tasks, and the associated treatment dosages, were effective for specific patients and patient populations (Dejong, Horn et al. 2004, Hart, Tsaousides et al. 2014, Van Stan, Roy et al. 2015, Turkstra, Norman et al. 2016). This can lead to, in some circumstances, prolonged courses of treatment, restoration of a voice that cannot be carried over into conversational use or a voice that does not meet the occupational or social requirements of the patients.

The rationale for this study is that the techniques employed in the CVT, have a clear, precise framework, that has well defined terms (Complete Vocal Institute, 2015; Sadolin, 2017) and has been evaluated using endoscopic, perceptual, acoustic and electroglottographic methods (McGlashan, Thuesen et al. 2017);(Thuesen, McGlashan et al. 2017);(Aaen, McGlashan et al. 2019, Aaen, McGlashan et al. 2020);(Aaen, McGlashan et al. 2021) for the singing voice. The CVT system has been used and continually developed over 35 years and now accounts for the largest agreeing group of singing teachers in the world. It is being used consistently in universities, conservatories, and in singing schools across Europe. It provides a structure and language that allows singers to create the voice quality they require in a healthy and sustainable way. It also allows singers to optimise vocal function and overcome unhealthy constrictive patterns, so the techniques lend themselves to patients with MTD. ‘Training programmes using CVT methodology have been developed to enable singers and singing teachers to improve their singing voice, achieve vocal goals and overcome technical issues many of which are due to unintentional hyper-constrictive muscle activity within the larynx and vocal tract. Voice therapy based on CVT principles (CVT voice therapy (CVT-VT)) has also been applied to professional speaking voice users and singers presenting with acute vocal problems leading to hoarseness or loss of voice when time is of the essence in getting a vocalist back to performing. This CVT-VT can help with deconstriction and improved voice production and projection. Although widely used by CVT-Ps CVT-VT has not been formally evaluated in performers or applied to non-performers although the principles of treatment of good voice production and deconstriction are applicable to both groups. If successful CVT-VT may provide SLT-VTs with additional tools to help manage patients with MDT.

### 3. THEORETICAL FRAMEWORK

The modes, sound colour and effects underpinning CVT have been studied using endoscopic, perceptual, acoustic and electroglottographic (EGG) analysis and each of these elements have been characterised (McGlashan, Thuesen et al. 2017, Thuesen, McGlashan et al. 2017, Aaen, McGlashan et al. 2021). There are similarities, but also significant differences, in vocal tract configuration between hyper-functional muscle tension dysphonia patterns and a healthy loud ('shouting') quality singing (Overdrive) and hypofunctional muscle tension dysphonia patterns and healthy production of a quiet breathy voice 'Neutral with air' (Saldias, 2019; Leppävuori et al, 2020). Similarities include a high vertical larynx position, small hypopharyngeal width, and epilaryngeal outlet. Differences include higher pitch, a wider lip and jaw opening, and larger volumes of the oral cavity (Saldias, 2019). Observation and anecdotal application by CVT teachers of non-singing dysphonic patients attending a Joint Voice Clinic has demonstrated that CVT methodology can be used successfully in a complimentary way to traditional SLT methods. CVT would be expected to achieve all the physiological aims as outlined in Table 1.

There is little literature of using singing therapy for patients with MTD or other types of dysphonia. However with more rehabilitation singing teachers and vocal coaches attending Voice Clinics and working closely with Speech Therapists, there is a general 'borrowing' and 'exchange' of techniques (Harris and Chalfin 2018). Vocal demands of singers and actors have similar requirements in voice and breath control, voice projection, overcoming stresses and avoidance of inappropriate hyper-constrictive muscle tension patterns as other professional voice users such as teachers, call centre workers. Therefore, potentially they can benefit from input from the specialised knowledge and experience of voice coaches and singing teachers. In addition, not infrequently singers' voice problems often stem from speaking voice problems.

### 4. RESEARCH QUESTION / AIM(S)

The aim of this proof-of-concept study is to evaluate whether the approach used in the Complete Vocal Technique to improve voice production in singers and performers can be applied to patients with Type I-III Muscle Tension Dysphonia pattern using a Telehealth medium.

#### 4.1. Objectives

SHORT TITLE/ACRONYM: CVT4MTD

IRAS:306954

The primary objective of this proof-of-concept study is to determine whether a CVT-VT approach improves vocal symptoms and function in patients with Type I-III Muscle Tension Dysphonia using a validated patient self-assessment questionnaire of the physical, functional and emotional aspects impact of the dysphonia.

Secondary objectives include:

- 1) to assess whether a CVT approach improves the voice, voice function and meets the goals of the therapy treatment from the patient perspective,
- 2) to assess whether a CVT approach meets the goals of the therapy treatment from and SLT-V and CVT-P perspective
- 3) to document and qualitatively evaluate the elements and/or techniques used in the treatment sessions and assess if or how they differ from mainstream SLT-VT techniques and give 'added value',
- 4) to assess a variety of secondary outcome measures for the treatment of MDT based on perceptual, acoustic and electroglottographic (EGG) assessments and self-reported measures to establish the best measures that reflect symptomatic, physiologically relevant, and patient-centred measures reflecting improvement in symptoms and daily function for patients
- 5) to evaluate the results with an aim of assessing the feasibility of performing a larger RCT.

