#### 4.2. Outcome

The main outcome measure is an improvement in the validated Voice Handicap Index self-assessment score following up to six sessions of therapy by an authorised CVT-P in patients with MTD ([Appendix 1](#))

Secondary outcome measures include:

- 1) A questionnaire to evaluate the acceptability of the approach to patients ([Appendix 2](#))
- 2) A questionnaire to evaluate the perceived effectiveness of the therapy from the Therapist's perspective. ([Appendix 3](#))
- 3) Qualitative comparison of the specific techniques used by the CVT-P based on a log of techniques used during the therapy session ([Appendix 4](#)) and qualitative assessment of anonymised, redacted transcripts of therapy sessions in those who have given additional consent
- 4) Comparison of pre- and post-treatment results of:
  - a. a range of simultaneously acquired acoustic and EGG measures made on voice recordings of continuous speech, phrases based on phonetically selected texts and sustained vowels ([Appendix B](#))

- b. psychoacoustic evaluation of the recorded voice samples using the CAPE-V ([Appendix 5](#)) and CVT derived assessment tools ([Appendix 6](#))
  - c. vocal tract discomfort scale – a self-reported rating scale ([Appendix 7](#))
  - d. change in the aerodynamic measure, the Maximum Phonation Time (MPT) ([Appendix 8](#))
- 5) Review of qualitative and quantitative results with recommendations on the feasibility and design of performing a larger RCT. The results will be published in a peer reviewed publication

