### Acoustic, EGG and MPT measures

Paired-samples t tests will also be applied to the secondary acoustic outcome measures (EGG, acoustic and MPT measures), together with 95% confidence intervals.

To control for Type 1 error of the primary outcome and secondary outcome analyses while maintaining an acceptable level of statistical power, the alpha level for all t-test comparisons will also be assessed at .025. Treatment effects will be assessed by comparing the pre-treatment to post-treatment change ( $\Delta$ ) scores, plotted as a forest plot in order to display the average  $\Delta$  change for each outcome measure and corresponding 95% confidence interval. Any significant treatment effects will be followed up with calculations of effect size using Cohen's d.

SHORT TITLE/ACRONYM: CVT4MTD

IRAS:306954

Measurement reliability for acoustic analyses will be calculated by reanalysis of 10% of the recordings. The recordings chosen for reliability analysis will be randomly selected from the total number of recordings. Pearson product–moment correlations will be used to assess inter-measurer and intra-measurer reliability of the acoustic and EGG measurements.

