### **CAPE-V**

For the secondary outcome measure CAPE-V, three experienced judges will be asked to rate all voice samples using the first four dimensions (overall severity, roughness, breathiness, and strain; on 100-mm visual analog scales (VAS) (Kempster et al, 2009). The judges will be blinded to pre- and post-treatment status of the voice samples. The voice samples will be presented in random order. The rating forms will be scored, and then scores for each subject will be averaged across the three judges. Average scores will be used for group analyses. Interrater agreement will be assessed using procedures described by Kreiman and Gerratt (1998). Agreement equivalent to within 1 point on a 7-point Equal Appearing Interval (EAI) scale will be calculated for each possible pair of raters for each voice sample. On a 100-mm visual analog scale, scores that fall within 7.2 mm will be considered to be in exact agreement on a 7-point EAI, and scores that are within 21.5 mm (7.2 + 14.3 mm) will be considered to be within 1 scale value. Two scores will be considered to agree if they fall within  $\pm 21.5$  mm on the VAS (probability of chance agreement  $p = 0.39$ ). The probability of agreement will be calculated by totaling all pairs of scores that agree and dividing by the total number of score pairs. Twenty percent of the voice samples will be randomly selected to be repeated for each judge. Repeat ratings will be used to assess intra-rater agreement, using the same calculation. To test for differences in the four CAPE-V dimensions, a multivariate analysis of variance will be applied to the pre-treatment to post-treatment change ( $\Delta$ ). Paired-samples  $t$  tests will also be applied to pre-treatment to post-treatment changes for each of the four dimensions within each group. A multiple comparison adjustment will be made for the four comparisons using the Bonferroni multiple-comparison procedure. The confidence intervals will be similarly adjusted for four comparisons, so the reported 95% confidence interval (CI) will actually be a 98.75% CI, which is a Bonferroni-adjusted CI.

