### **Other Questionnaires**

Comparison of the total score of the frequency and the total score of the severity of symptoms evaluated in the Vocal Tract Discomfort (VTD) scale pre- and post-treatment will be compared using paired sample  $t$ -tests. The comparison of the frequency and the severity of particular symptoms of the VTD scale pre- and post-treatment will be made by means of the non-parametric Mann – Whitney  $U$  test. Comparison of the frequency and the intensity of particular VTD items in the respective subgroups of patients pre- and post-treatment using ANOVA. Finally, the relationships between the results of the VTD scale and VHI and MPT will be estimated by means of the Pearson  $r$  coefficient. Other non-validated questionnaires will be reported using descriptive statistics.

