### 7.2.1. Size of sample

As this is a proof-of-concept study the sample size of ten patients was selected arbitrarily to generate the necessary results for a power analysis for future studies.

SHORT TITLE/ACRONYM: CVT4MTD

IRAS:306954

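### Secondary objective 4 sets out to establish the best of at least nine measures in ten patients without defining best, and Cohen's d is calculated only for significant results, which inflates the effects that are reported.

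*Combined protocol and SAP*

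**What the plan says.** Section 4.1, secondary objective 4, sets out to assess perceptual, acoustic, electroglottographic (EGG) and self-reported outcomes "to establish the best measures that reflect symptomatic, physiologically relevant, and patient-centred measures". Neither section 4 nor section 5 says what makes a measure best.

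The candidates are in sections 4.2 and 5:
- "a range of simultaneously acquired acoustic and EGG measures made on voice recordings of continuous speech", phrases and sustained vowels. The number is left to Appendix B, which is not part of the documents available.
- CAPE-V, "using the first four dimensions (overall severity, roughness, breathiness, and strain".
- The Vocal Tract Discomfort (VTD) scale, "total score of the frequency and the total score of the severity of symptoms", plus single items.
- "change in the aerodynamic measure, the Maximum Phonation Time (MPT").
- "CVT derived assessment tools", number not given.

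Under Acoustic, EGG and MPT measures, section 5 sets an alpha of .025 for all t tests and plans a forest plot of mean change with 95% CI for each outcome. It then says: "Any significant treatment effects will be followed up with calculations of effect size using Cohen's d". Although placed under a secondary-outcome heading, this paragraph also speaks of the primary outcome, so the rule appears to cover the Voice Handicap Index (VHI) as well.

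Section 7.2.1 says that "the sample size of ten patients was selected arbitrarily to generate the necessary results for a power analysis for future studies". Section 4.2, item 5, takes the results into recommendations on the feasibility and design of a larger RCT.

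**The concern.** There are two linked problems.

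The first is written into the plan. If d is calculated only when a result is significant, the published d values are a selected subset. In a sample of ten the selection is severe, because only a large observed effect can reach significance. The study's stated purpose is to supply inputs to a power analysis, and effect sizes filtered in this way would make a later trial too small.

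The second is a gap. To establish the best measures is a claim about comparison between outcomes, but there is no criterion, no method of comparison and no statement of how uncertain the comparison would be. If someone later fills the gap by taking the measure with the largest effect, chance plays a large part in the choice, and the winner's effect is overstated again.

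**Working it through.** **Inputs from the documents.** n = 10 (section 7.2.1); paired t tests with alpha .025 (section 5); d only after significance (section 5). Candidates that can be counted: CAPE-V 4 + VTD totals 2 + MPT 1 + acoustic at least 1 + EGG at least 1 = at least 9. The sample size has no inputs, so there is no planned figure to reproduce.

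**Assumptions, not in the documents.** Two-sided tests; normally distributed changes; d = mean change / SD of change (the plan does not say which SD is used).

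**Step 1: the smallest d that can be reported.** For a paired test, t = d × √n. The critical value on 9 df at two-sided .025 is 2.685, so |d| must reach 2.685 / √10 = 2.685 / 3.162 = 0.849.

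**Step 2: what the filter does.** Power is from the non-central t. The mean reported d is from simulation, keeping only studies beyond the threshold.

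| True d | Power at .025 | Mean d when reported | Ratio to truth |
|---|---|---|---|
| 0.50 | 19% | 1.13 | 2.3 |
| 0.65 | 32% | 1.17 | 1.8 |
| 0.80 | 47% | 1.22 | 1.5 |

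The text says that comparisons will *also* be assessed at .025, so a reader might use .05. The threshold is then 0.715, and true values of 0.5 and 0.8 are reported as 1.01 and 1.12 on average (2.0 and 1.4 times). The conclusion does not change.

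Part of the excess is ordinary small-sample bias in d, about 9% at n = 10. The usual correction is 1 − 3/(4 × 9 − 1) = 0.914. It does not cure the selection: 1.13 × 0.914 = 1.03, still about twice a true 0.5.

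**Step 3: consequence for a power analysis.** Required sample size varies as 1/d². If a filtered d were carried over, the planned size relative to the size needed would be (0.5/1.13)² = 0.20, (0.65/1.17)² = 0.31 or (0.8/1.22)² = 0.43. This illustrates scale only: an RCT needs a between-group effect, which this single-arm study does not give.

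**Step 4: ranking, if it were done by observed d.** Simulated with n = 10, true d evenly spaced from 0.2 to 0.8, and a common correlation between change scores.

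| Measures | Correlation | Top measure truly best | Observed / true d of the top measure |
|---|---|---|---|
| 10 | 0 to 0.5 | 25–31% | 2.0 to 1.7 |
| 10 | 0.9 | 51–52% | 1.3 |
| 20 | 0 to 0.5 | 14–18% | 2.3 to 1.9 |
| 20 | 0.9 | 31–32% | 1.4 |

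Over a wider grid (5 to 30 measures, correlation 0 to 0.9, several patterns of true effect), the top measure is truly best in 12% to 99% of studies where a best measure exists, and the inflation is about 1.1 to 3.0 times. The high end arises where change scores are strongly correlated and one measure is clearly ahead.

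**Step 5: ranking by correlation with VHI change instead.** With ten measures, one true r of 0.6 and the rest 0.3, the best is picked 37% of the time, and the top observed r averages 0.73 against a true 0.41 for the measure picked. That criterion is no more stable at n = 10.

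**The case against.** The strongest reply is that the plan does more than test and report d. Section 5 has a forest plot of mean change with 95% CI for each outcome, significant or not; inter- and intra-measurer reliability for acoustic and EGG measures; inter- and intra-rater agreement, a multivariate test and Bonferroni-adjusted intervals for CAPE-V; and correlations of VTD with VHI and MPT. Section 4.2 adds a joint review of qualitative and quantitative results. All of this stands. A reader of the forest plot could even recover d: with n = 10, the SD of change is the half-width of the interval × 3.162 / 2.262 = 1.40 half-widths. But the plan does not say that the plotted changes are standardised, so measures in different units cannot be compared directly, and the d values actually presented remain the filtered ones.

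A second reply is that the objective speaks of measures in the plural and of symptomatic, physiological and patient-centred relevance, which is not a contest for the largest effect. That also stands. A reader might infer that the study will name the measure with the largest d; no section says so. What the documents support is that the criterion is missing.

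Third, missing the single best measure may do little harm. In the evenly spaced scenario at correlation 0.3, the selected measure's true d lies within 0.2 of the best in 77% of studies (10 measures) or 73% (20), and averages about 0.66 or 0.65 against 0.50 for a random pick. It would be unfair to call the choice pure noise.

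Fourth, VHI is the pre-specified primary outcome. A reader might infer that the RCT would take over a top-ranked secondary measure and its d; section 7.2.1 says only that the results feed a power analysis.

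**Conclusion.** The point holds for what the plan states. Calculating d only after significance means that no |d| below about 0.85 is reported at two-sided .025, and true effects of 0.5 to 0.8 appear as 1.13 to 1.22 on average. This needs no assumption about the number of measures or their correlation. It does rest on two-sided testing, roughly normal changes and d scaled by the SD of change; with another scaling the threshold moves, but selection on significance still inflates. It works against the purpose given for the sample size.

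It also holds that ten patients cannot establish the best among nine or more outcomes when best is undefined.

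The tempting stronger statement, that the top-ranked measure is usually wrong and its effect doubled, is not supported as a general result. It describes ranking by d with low to moderate correlation and modest differences between measures. The number of measures, their correlations and their true effects are not in the documents, and the results range from 12% to 99% correct and from about 1.1 to 3.0 times inflation.

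**What to change.** 1. In section 5, replace the rule that d follows significance. Report for every measure, significant or not, the standardised mean change with its 95% CI, with the small-sample correction, beside the planned forest plot of raw changes. State which SD is used.
2. In section 4.1, reword objective 4 as describing the responsiveness of candidate measures, and state that ten patients do not rank them, whether by effect size or by correlation with VHI change.
3. In section 4.2, item 5, say that measures for the RCT will be chosen on reliability and relevance, and that the RCT will not be sized on a d selected for being significant or largest.

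No patients, visits or assessments are added. The cost is a longer results table and a weaker claim for objective 4.
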